### 3.8.4. Subgroup Analyses

Differences in treatment efficacy will be explored in several pre-defined subgroups: site, age (median split), screening MoCA total score (median split), baseline LEDD (median split), and baseline cholinesterase inhibitor (donepezil vs. rivastigmine). Subgroup specific estimates will be obtained by including subgroup, subgroup  $\times$  visit, and subgroup  $\times$  treatment  $\times$  post-baseline visit terms to models for primary and key secondary efficacy outcomes based on the mITT sample.

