3.1.2 Planned Number of Patients and Sites

Approximately, 120 patients will be screened, assuming a 33% screen failure rate, to randomize 80 patients.

Approximately 12 sites will participate in the study.

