### **2.3. Study Population**

Individuals eligible for trial participation are men or women at least 50 years old who have received a diagnosis of probable PDD according to the Movement Disorder Society Task Force clinical diagnostic criteria for dementia associated with Parkinson's disease ([Emre et al. 2007](#)) and who are taking a cholinesterase inhibitor. Detailed inclusion and exclusion criteria are specified in the clinical protocol.

Participants will be recruited from a total of 20 clinical sites located through the US.

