### **2.5. Treatment Allocation**

At the baseline visit, eligible participants are randomly allocated in equal proportion to one of two treatment groups, SYN120 100 mg QD or placebo, according to a permuted-block randomization schedule with a block size of 4, stratified by site. The randomization schedule was prepared by computer program by the unblinded study statistician. Stratification by site is achieved by distributing to sites allotments of study drug kits that consist of a full block from the permuted-block schedule.

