### **3.8.5. Multiplicity Adjustments**

A single primary efficacy outcome is specified with a single treatment comparison and a pre-specified primary analysis with no interim analysis. Therefore, no multiplicity exists for the primary analysis, and inference will be based on two-tailed testing at alpha = 0.05. If the primary analysis is significant, then testing the key secondary outcome at alpha = 0.05 maintains an overall type I error rate at 5% under a closed testing sequential analysis. When the primary analysis is not significant, we limit the overall type I error rate to 10% or less (depending on the magnitude of correlation between the primary and key secondary outcomes) when significance of the key secondary outcome alone is accepted as evidence of a therapeutic benefit from SYN120. Results from analysis of non-key secondary efficacy endpoints, exploratory efficacy endpoints, and subgroup analyses will report nominal, comparison-wise p-values, recognizing that the totality of results will be evaluated in judging the potential of SYN120 as a therapeutic agent for PDD.

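### Age, screening MoCA and baseline LEDD are tested as effect modifiers only through median splits, which loses efficiency when the interaction is roughly linear; continuous terms would use no more coefficients

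*SAP*

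**What the plan says.** SAP 3.8.4 opens with "Differences in treatment efficacy will be explored in several pre-defined subgroups". Its list includes "site, age (median split), screening MoCA total score (median split), baseline LEDD (median split") and baseline cholinesterase inhibitor. One recipe serves all five factors: "Subgroup specific estimates will be obtained by including subgroup", its interaction with visit, and its interaction with treatment and post-baseline visit. These terms go into the primary and key secondary models on the mITT sample.

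Three other places matter:

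- SAP 3.8.5 limits the inferential weight: "subgroup analyses will report nominal, comparison-wise p-values".
- SAP 3.8.1 already carries site as a random intercept. SAP 3.8.4 does not say whether that term stays when site is the subgroup, nor whether the subgroup terms are fixed.
- The site counts differ. SAP 2.3 has "Participants will be recruited from a total of 20 clinical sites"; Protocol 3.1.2 has "Approximately 12 sites will participate in the study".

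**The concern.** All three split variables are recorded on numeric scales: age in years, MoCA as a 0-30 total (SAP 3.3.9) restricted to 10-23 at entry (Protocol 4.1), and LEDD as a computed daily milligram dose (SAP 3.3.12). Splitting at the median treats a patient just above the cut like one at the far end of the range. Unless the treatment effect really jumps near the median, this weakens the interaction test in a trial of about 80 patients, where interaction tests are already weak. The cut-points also depend on who enrols, so the estimates do not carry over directly to another sample.

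A lesser matter is site. Given the same recipe as a two-level factor, site generates many coefficients and leaves very few patients behind each site-specific effect.

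**Working it through.** **The plan's own figure.** SAP 3.4 and Protocol 10.8 give 80 randomized, 15% loss, effect size 0.69, two-sided alpha 0.05, and at least 80% power by a two-sample t-test. Evaluable per arm: 80 x 0.85 / 2 = 34. The noncentrality is 0.69 x sqrt(34/2) = 2.84 on 66 degrees of freedom, which gives power 80.05%. The figure reproduces. The documents give no power or precision for the subgroup models.

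**Information kept by a median split.** For a linear interaction, the relative efficiency is the squared correlation between the modifier X and the indicator that X exceeds its median. For normal X this is 2/pi = 0.637, a loss of 36.3%. On that scale 80 patients count as 80 x 0.637 = 51.

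The documents do not give the distributions, so the shapes below are assumptions:

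| Assumed modifier | Loss |
|---|---|
| Uniform | 25% |
| MoCA limited to 10-23 (uniform, or truncated normal with mean 18, SD 3-5) | about 25-33% |
| Near-normal age, at least 50 | about 36% |
| Right-skewed LEDD (lognormal, sigma 0.4-0.8) | 44-63% |
| True threshold at the median | none |

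**Effect on power.** Suppose the continuous test has 80% power, so the expected z is 1.96 + 0.84 = 2.80. After a split that loses a fraction L, power is Phi(2.80 x sqrt(1 - L) - 1.96).

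- L = 0.363 (normal): Phi(2.235 - 1.960) = 61%.
- L = 0.25 to 0.33: 68% to 63%.
- L = 0.44 to 0.63: 55% to 40%.

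**Cost in coefficients.** The primary model has 5 fixed coefficients: 3 visit means and 2 post-baseline treatment effects. A two-level split doubles this to 10. A continuous modifier adds 1 (covariate) + 2 (by visit) + 2 (by treatment by post-baseline visit), also making 10.

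**Site, if entered as fixed terms.** Each site needs 3 visit means and 2 treatment effects, so S sites need 5S coefficients: 100 for 20 sites, 60 for 12. A rank check of the design matrix gives the same counts. The data are at most 80 x 3 = 240 observations. With residual SD 1 and even enrolment:

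- 20 sites: 80 / 20 = 4 patients, 2 per arm; SE = sqrt(1/2 + 1/2) = 1.0 SD, 95% interval about +/-2.0 SD.
- 12 sites: 80 / 12 = 6.67 patients, 3.33 per arm; SE = sqrt(2 / 3.33) = 0.77 SD, 95% interval about +/-1.5 SD.
- Whole trial: sqrt(2/40) = 0.22 SD. The design effect is 0.69.

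With 20 sites of 2 per arm and 15% random loss, a site keeps both arms at Week 16 with probability (1 - 0.15^2)^2 = 0.956. The chance that at least one site loses an arm is 1 - 0.956^20, about 60%.

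**Would a random site-by-treatment term do better?** A balanced ANOVA approximation without dropout takes a true between-site SD of the effect of 0.35 (an assumption). With 20 sites the variance estimate is zero about 40% of the time and power to detect heterogeneity is about 9%; with 12 sites, about 39% and 12%.

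**The case against.** The strongest reply is that nothing decisive depends on this. The SAP calls the subgroup work exploration and attaches nominal p-values, the median rule is set in advance, and the cut uses covariate values only, so it gives no room for outcome-driven cut-points. All of that stands, and it keeps the point minor. It does not make the split the better test, because the continuous version needs no extra data or coefficients.

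It is also fair that the continuous fit relies on approximate linearity and that a few very high LEDD values could carry much leverage. That calls for a linearity check and, if needed, a transformation.

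A reader might infer several stronger things that the documents do not support:

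- **A 36% loss for all three modifiers.** It is not a document figure. It needs a normal modifier and a linear interaction, and other shapes give quite different losses.
- **A subgroup plan that fits 100 coefficients to 80 patients.** That count belongs to the site model alone, with 20 sites and fixed terms. The other four subgroup models have 10 coefficients each. The site model uses up to 240 repeated observations and is estimable if every site has both arms at each post-baseline visit.
- **Many sites with one arm only.** SAP 2.5 specifies a "permuted-block randomization schedule with a block size of 4, stratified by site", so any site that randomizes three or more patients has both arms. One-arm sites arise from very low enrolment or dropout.
- **Site definitely entered as fixed.** This is inferred from the common recipe and the promise of subgroup-specific estimates; the SAP does not use the word.
- **A subgroup result that will select the next trial's population.** Neither document says so.

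**Conclusion.** The point holds as a modest, cheap improvement. Testing age, MoCA and LEDD only through median splits is less efficient than a continuous test unless the true effect is a threshold near the median, and the SAP gives no reason to expect one. Under linearity and a normal modifier the loss is about 36% of the information (power 80% to about 61%). The assumed range runs from about 25% to over 60%, depending on the variable's shape. Primary inference and the sample size are untouched.

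The site note is secondary. Under either site count the site-specific effects are close to uninformative, because their intervals are more than twice the design effect on each side. The limit is about 80 patients spread over many sites, and no model term removes it. Keeping the random site intercept beside fixed site terms would be redundant but would not bias the estimates.

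**What to change.** In SAP 3.8.4:

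1. Make the interaction test for age, screening MoCA and baseline LEDD continuous, with covariate, covariate by visit, and covariate by treatment by post-baseline visit terms. State a linearity check, and a transformation of LEDD if it is skewed. Keep the median splits for display only.
2. Label site-specific estimates as descriptive. Alternatively, use a random site-by-treatment term and acknowledge its low power.
3. Say whether site enters as fixed or random, and drop the random site intercept if the site terms are fixed.
4. Reconcile the site counts in SAP 2.3 and Protocol 3.1.2.

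The cost is SAP wording and model terms. No data collection, sample size or primary analysis changes. The small downside of item 1 is its reliance on approximate linearity and the leverage of extreme LEDD values. Item 2 is the more debatable part, and item 1 does not depend on it.

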### **3.8.5. Multiplicity Adjustments**

A single primary efficacy outcome is specified with a single treatment comparison and a pre-specified primary analysis with no interim analysis. Therefore, no multiplicity exists for the primary analysis, and inference will be based on two-tailed testing at alpha = 0.05. If the primary analysis is significant, then testing the key secondary outcome at alpha = 0.05 maintains an overall type I error rate at 5% under a closed testing sequential analysis. When the primary analysis is not significant, we limit the overall type I error rate to 10% or less (depending on the magnitude of correlation between the primary and key secondary outcomes) when significance of the key secondary outcome alone is accepted as evidence of a therapeutic benefit from SYN120. Results from analysis of non-key secondary efficacy endpoints, exploratory efficacy endpoints, and subgroup analyses will report nominal, comparison-wise p-values, recognizing that the totality of results will be evaluated in judging the potential of SYN120 as a therapeutic agent for PDD.

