10.4.2 Key Secondary Efficacy Analyses

The key secondary efficacy variable will be analyzed in the mITT sample using the model specified for the primary analysis of the primary efficacy variable. Treatment-dependent differences in the change from Baseline to Week 16 on the CDR Quality of Episodic Memory will be estimated by linear contrasts and tested using a two-tailed Wald-test at alpha = 0.05. Equivalent sensitivity analyses as are planned for the primary efficacy variable will be applied to the key secondary efficacy variable.

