10.4.3 Multiplicity Adjustment for Primary and Key Secondary Endpoints

If the effect of SYN120 on the primary outcome in the mITT sample is significant at alpha = 0.05, then testing the key secondary outcome at alpha = 0.05 maintains an overall type I error rate at 5% under a closed testing sequential analysis. When the primary analysis is not significant, we limit the overall type I error rate to 10% or less (depending on the magnitude of correlation between the primary and key secondary outcomes) when significance of the key secondary outcome alone is accepted as evidence of a therapeutic benefit from SYN120.

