## 1. INTRODUCTION

This Statistical Analysis Plan (SAP) defines the analysis samples, specifies the analysis, and guides the interpretation of results from the [SYN120-CL03](#) or SYNAPSE clinical trial. The SAP supplements the clinical protocol. Readers are encouraged to refer to the clinical protocol for details on the rationale for the intervention, eligibility criteria, conduct of the trial, clinical assessments and the timing of their use in the trial, definitions and reporting of adverse events, data management conventions, and regulatory oversight and compliance procedures. The reader is referred to the Investigator's Brochure for additional details on physiochemistry and pre-clinical and clinical pharmacokinetics and safety of the investigational product, SYN120.

In case of discrepancies between the SAP and the clinical protocol concerning matters of analysis, the SAP is authoritative. On all other matters, the clinical protocol is authoritative.

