estimate "0|Placebo|Wk  08" intercept 1 visit  0 1 0 post*trtrnd*visit 0 0 0  0 1 0 / cl;
estimate "0|Placebo|Wk  16" intercept 1 visit  0 0 1 post*trtrnd*visit 0 0 0  0 0 1 / cl;
estimate "1|Placebo|dWk 08" intercept 0 visit -1 1 0 post*trtrnd*visit 0 0 0  0 1 0 / cl;
estimate "1|Placebo|dWk 16" intercept 0 visit -1 0 1 post*trtrnd*visit 0 0 0  0 0 1 / cl;
estimate "2|ActvPlb|dWk 08" intercept 0 visit  0 0 0 post*trtrnd*visit 0 1 0  0 -1 0 / cl;
estimate "2|ActvPlb|dWk 16" intercept 0 visit  0 0 0 post*trtrnd*visit 0 0 1  0 0 -1 / cl;
```

The estimate labeled "2|ActvPlb|dWk 16" specifies the primary hypothesis. A significant mean improvement over 16 weeks in CDR COA among participants randomized to SYN120 relative to mean changes among participants randomized to placebo would be considered evidence of therapeutic benefit from SYN120.

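### Does SAP 3.8.5 misstate the overall type I error rate as 5% when the key secondary outcome can be claimed without the primary?

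*SAP*

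**What the plan says.** For the primary outcome (CDR Continuity of Attention), SAP 3.8.5 notes that there is one outcome, one comparison and no interim look, so that "inference will be based on two-tailed testing at alpha = 0.05".

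It then turns to the key secondary outcome: "If the primary analysis is significant, then testing the key secondary outcome at alpha = 0.05 maintains an overall type I error rate at 5"%. The rest of that sentence attributes the figure to closed sequential testing. The sentence after it covers the other case: "When the primary analysis is not significant, we limit the overall type I error rate to 10% or less", with the exact value depending on the correlation between the two outcomes, "when significance of the key secondary outcome alone is accepted as evidence of a therapeutic benefit from SYN120".

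Protocol 10.4.3 is nearly the same. Only the opening of its 5% sentence differs: "If the effect of SYN120 on the primary outcome in the mITT sample is significant at alpha = 0.05, then testing the key secondary" outcome at the same level again gives 5%.

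The sections that specify the key secondary analysis make it unconditional. Under Protocol 10.4.2 its treatment difference is "estimated by linear contrasts and tested using a two-tailed Wald-test at alpha = 0.05", whatever the primary shows. SAP 3.8.3 applies the primary's models and adds no condition. On any difference between the documents, SAP section 1 settles the order: "In case of discrepancies between the SAP and the clinical protocol concerning matters of analysis, the SAP is authoritative".

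**The concern.** A familywise error rate belongs to a decision rule fixed before the data are seen. It cannot be 5% when the primary succeeds and 10% when it fails. A fixed sequence holds 5% because a failed primary ends confirmatory testing, and here the next sentence removes that stop. What the plan adopts is therefore two tests, each at two-sided 0.05, either of which may support a claim of benefit.

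If the 5% were taken as a property of that rule, it would understate the rate by up to a factor of two. The practical worry is the study report. After a significant primary, an author could cite SAP 3.8.5 for 5% control across both outcomes, although the rule never had that control.

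**Working it through.** **Inputs.** Two-sided 0.05 for the primary (SAP 3.8.5) and for the key secondary (Protocol 10.4.2). No interim analysis (SAP 3.7), so no other alpha is spent. The correlation r between the two test statistics is not given, so a range is assumed, with the statistics taken as jointly normal.

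**The plan's figures**

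- *Strict sequence* (key secondary claimed only after a significant primary). With both nulls true, any false claim requires a false rejection of the primary, so the rate is P(primary rejects) = 0.05. This reproduces the stated 5%.
- *Key secondary accepted on its own.* The Bonferroni bound is 0.05 + 0.05 = 0.10. This reproduces the stated 10% or less.

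**Rate of the rule as adopted, both nulls true**

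P(at least one rejection) = 0.05 + 0.05 − P(both), where P(both) = 0.05 × P(secondary rejects given primary rejects). The secondary-only share is this total minus 0.05.

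| r | P(secondary given primary) | P(both) | At least one | Secondary only |
|---|---|---|---|---|
| 0 | 0.0500 | 0.0025 | 0.0975 | 0.0475 |
| 0.3 | 0.0976 | 0.0049 | 0.0951 | 0.0451 |
| 0.5 | 0.1851 | 0.0093 | 0.0907 | 0.0407 |
| 0.7 | 0.3310 | 0.0165 | 0.0835 | 0.0335 |
| 0.9 | 0.5929 | 0.0296 | 0.0704 | 0.0204 |

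A simulation of 2 million draws gave 0.0976 at r = 0 and 0.0907 at r = 0.5. The two-sided result does not depend on the sign of r. The stated ceiling of 10% is met throughout.

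**Where the excess arises.** The route through a significant primary contributes 0.05 in every row. Everything above 5% comes from the secondary-only route, which is the route to which the SAP attaches its 10% statement.

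**Only one null true.** The sole possible error is rejecting that null, so the adopted rule has a rate of 0.05. With the primary truly effective at 80% power and r = 0, the strict sequence would give 0.80 × 0.05 = 0.04 for the secondary, against 0.05 as adopted. Neither exceeds 5%.

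**Direction.** For the primary, SAP 3.8.1 treats only improvement as benefit: "A significant mean improvement over 16 weeks in CDR COA among participants randomized to SYN120" relative to placebo. Applying that to both outcomes, at 0.025 each, the chance of at least one false claim in favour of SYN120 is 1 − 0.975² = 0.0494 at r = 0, 0.0454 at r = 0.5 and 0.0417 at r = 0.7. The bound is 0.025 + 0.025 = 0.05. The strict sequence would give 0.025.

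**The case for a change.** The best case for a change is that the 10% is disclosed only for a non-significant primary. A reader with a significant primary is pointed to the 5% sentence, and nothing there says that 5% needs a stop which the following sentence takes away. One or two sentences would cure this at almost no cost, and the overall rate reported would then be the same whatever the primary shows.

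Part of this stands. Tying an overall rate to the observed primary result is loose wording, and the adopted rule does have one rate, at most 10%.

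The claim that the 5% is wrong does not stand. The sentence is conditional on a significant primary and names closed sequential testing, the procedure for which 5% is correct. The chance of a significant primary together with a false claim on either outcome is also at most 5%: it is 0.05 if the primary null is true, and P(both reject), which cannot exceed 0.05, if only the secondary null is true. To quote 5% for the unrestricted rule, an author would have to pass over the very next sentence. Neither document says that 5% will be reported for the pair.

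**Conclusion.** The point is editorial and calls for no change. SAP 3.8.5 sets two figures side by side, each correct for its own procedure: 5% for a strict sequence, and at most 10% when the key secondary alone suffices. A statistician reading the paragraph would take at most 10% as the overall two-sided rate of the rule as adopted.

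Across the correlations assumed here that rate runs from 9.75% (r = 0) down to 7.0% (r = 0.9). The excess over 5% exists only if both nulls are true. The exact value cannot be fixed without the correlation, but the 10% bound needs neither the correlation nor joint normality.

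Accepting the key secondary alone at a disclosed higher error rate is a fair trade-off in a phase 2a trial of preliminary efficacy, and the primary's own level is stated separately and is unaffected. A sponsor following the text as it stands would run the same tests and reach the same conclusions as under any rewording.

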### **3.8.6. Missing Data**

Baseline values for efficacy endpoints will be determined from the last non-missing data collected prior to the first dose of study medication. The planned repeated-measures model yields estimates that are unbiased conditional on the observed scores under a missing at random assumption. In addition, a secondary analysis of the primary endpoint will use placebo-based multiple imputation of missing data. The Cochran-Mantel-Haenszel row mean score LOCF and WO analyses provide estimates of treatment effect when normality assumptions are violated. Additional sensitivity analyses may be pursued to impute missing values or otherwise construct models for unobserved outcomes if more than 20% of participants are missing follow-up data for any reason.

### **3.8.7. Clinical Interpretation**

Unadjusted summary statistics by treatment group and visit and estimates from the shared-baseline, mixed model analyses for all CDR measures will be provided to [name] by the study statistician. [name] will provide a clinical interpretation of the effects of SYN120 based on treatment-dependent effects on the CDR measures. This clinical interpretation will supplement the numerical and statistical results.

## **3.9. Safety Analysis**

### **3.9.1. Treatment-emergent Adverse Events**

The incidence of TEAEs will be summarized by the number of events of a given classification experienced by participants in each treatment group and by the number and proportion of participants experiencing such an event in each treatment group in the ST sample. TEAEs will be summarized in aggregate across all MedDRA terms and separately by MedDRA term.

Aggregate summaries of TEAE incidence will include: (a) any TEAE, (b) any severe TEAE, (c) any serious TEAE, (d) any TEAE at least possibly related to study drug, (e) any TEAE leading to permanent study drug discontinuation or early termination from the trial, and (f) any TEAE resulting in death. Aggregate summaries will be presented by treatments for event rates and proportion of participants.

Aggregate summaries of TEAE grade will include characteristics of: (a) seriousness, (b) severity, (c) relatedness to study drug, (d) action taken with study drug, and (e) outcome. For each level of a given TEAE characteristic, summaries will include the number of events of a given classification and by the number and proportion of participants for which that level of a characteristic was the worst they experienced (treating any unknown characteristic as not worst).

TEAEs will also be summarized separately by MedDRA term at three levels: (a) System Organ Class, (b) High Level Term, and (c) Preferred Term. At each level, the number of events of a given classification and the number and proportion of participants experiencing such an event will be summarized for each treatment group.

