10.8 Determination of Sample Size

A total sample size of 80 or 40 in each group will provide at least 80% power to detect a true treatment difference equal to an effect size of 0.69 assuming up to 15% loss to follow up and using a two-tailed test at alpha = 0.05 based on a simple two-sample t-test. Additional power will be obtained from the proposed analysis using a shared-baseline repeated measures ANOVA.

Approximately 120 patients will be screened, assuming a 33% screen failure rate, to randomize 80 patients.

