### 3.2.2. Safety Endpoints

The following safety endpoints will be evaluated:

- Proportion of participants experiencing the following and event rates relative to time at risk of: (a) any treatment-emergent AE (TEAE), (b) any severe TEAE, (c) any serious TEAE, (d) any TEAE at least possibly related to study drug, (e) any TEAE leading to permanent study drug discontinuation or early termination from the trial, and (f) any TEAE resulting in death, summarized across all MedDRA terms
- Proportion of participants experiencing and number of unique events of all TEAEs classified by seriousness, severity, relatedness to study drug, action taken with study drug, and outcome, summarized across all MedDRA terms
- Proportion of participants experiencing and number of unique events of each type of TEAE and serious TEAE classified by MedDRA system organ class, high level term, and preferred term
- Proportion of participants experiencing treatment-emergent orthostatic hypotension
- Mean 16-week change from baseline in supine and standing SBP, supine and standing DBP, and differences from supine to standing SBP and DBP
- Mean 16-week change from baseline in weight
- Proportion of participants experiencing treatment-emergent clinically significant laboratory abnormalities classified by assay, whether the abnormality is below or above the normal range, and visit, with cross-classification of frequencies of abnormalities from baseline to each scheduled post-baseline visit at which safety labs are performed
- Mean 16-week change from baseline in laboratory assays
- Proportion of participants experiencing treatment-emergent clinically significant ECG abnormalities
- Mean 16-week change from baseline in ECG parameters
- Mean 16-week change from baseline in UPDRS Part I score, II score, III score, I through III total score, Part IV dyskinesia score, Part IV clinical fluctuations score, Part IV other complications score, and Part IV total score
- Mean 16-week change from baseline in levodopa daily dosage (LDD) and levodopa equivalent daily dosage (LEDD)
- Proportion of participants reporting any treatment-emergent suicidal ideation
- Maximum post-baseline suicidal ideation planning, frequency, duration, controllability, deterrents, and reasons

- Proportion of participants reporting any post-baseline suicidal behavior, actual attempts, non-suicidal self-injurious behavior, interrupted attempts, aborted attempts, preparatory acts or behaviors, or completed suicide

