- Maximum post-baseline suicidal behavior lethality and potential lethality

Reported proportions will use as their denominator all participants in the Safety and Tolerability sample (see [Section 3.5](#) below).

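### In the participant-level worst-grade adverse event summary, an unknown attribute ranks below every known one, so the worst grade can be understated but never overstated, and no sensitivity summary shows by how much

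*SAP*

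**What the plan says.** SAP 3.9.1 plans three families of TEAE summary: incidence, grade, and counts by MedDRA term. The rule at issue sits in the second. "Aggregate summaries of TEAE grade will include characteristics of: (a) seriousness, (b) severity, (c) relatedness to study drug, (d) action taken with study drug", with outcome as the fifth item.

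Two things are reported for each level of each characteristic. The first is at event level: "For each level of a given TEAE characteristic, summaries will include the number of events of a given classification". The second is at participant level: how many people, and what share, are those for whom "that level of a characteristic was the worst they experienced (treating any unknown characteristic as not worst". Only the second depends on how levels are ranked.

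The incidence family is listed separately and includes "b) any severe TEAE, (c) any serious TEAE, (d) any TEAE at least possibly related to study drug". SAP 3.2.2 names the same quantities as safety endpoints, for example "any TEAE at least possibly related to study drug". Neither section says how an event of unknown severity or relatedness enters these counts. SAP 3.2.2 also lists the classification by the five characteristics as an endpoint and fixes the denominator: "Reported proportions will use as their denominator all participants in the Safety and Tolerability sample".

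The SAP's missing-data section (3.8.6) belongs to the efficacy analysis and opens accordingly: "Baseline values for efficacy endpoints will be determined from the last non-missing data collected prior to the first dose of study medication". It gives no rule for incomplete adverse event attributes. Protocol 10.5.1 gives none, and Protocol 10.7 deals with withdrawal and missing outcome data.

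**The concern.** A worst-level table is meant to show how bad things became for each participant. Ranking unknown below every known level means that whatever is missing is resolved at or below the worst level already seen. A person with a mild event and an ungraded event appears as mild, with nothing in that column to show that a second event could not be graded.

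Safety and tolerability are stated objectives, and the arms are small, so a few such participants would visibly change a reported proportion. The efficacy side is treated differently. SAP 3.8.2 includes a worst-observed imputation and a placebo-based multiple imputation for missing primary endpoint data. For adverse event attributes the only stated convention is the reassuring one, and nothing tests it.

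**Working it through.** The documents state no figure for this rule, so there is none to reproduce. The check applies the rule to small sets of events and then finds the weight of one participant.

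**Inputs**
- Ranking rule and the five characteristics: SAP 3.9.1.
- Denominator: the Safety and Tolerability sample, SAP 3.2.2.
- Planned size: Protocol 10.8, "A total sample size of 80 or 40 in each group will provide at least 80% power". I use n = 40, assuming every randomized participant enters that sample.
- Number of participants with an unknown attribute: not in the documents. I assume k = 1 to 4 per arm, for illustration only.

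**Step 1: the rule applied to severity**

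| Participant's events | SAP rule | With a separate unknown row |
|---|---|---|
| mild, unknown | mild | unknown |
| mild, mild, unknown | mild | unknown |
| moderate, unknown | moderate | unknown |
| severe, unknown | severe | severe (already at the top level) |
| unknown only | unknown (no known level to use) | unknown |

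By the same logic, {unrelated, unknown} becomes unrelated and {related, unknown} stays related. {recovered, unknown} becomes recovered if recovered is the lowest outcome level. The SAP does not state the order of levels for outcome or action taken, so that last example is an assumption.

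**Step 2: direction**

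When at least one level is known, the true worst level is the higher of the worst known level and the true value of the unknown event. The SAP reports the worst known level. The reported grade is therefore equal to or lower than the true one. It is lower only if the unknown event was truly worse than the worst known event.

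**Step 3: weight of one participant**

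Shift in a category proportion = k/n.
- k = 1: 1/40 = 2.5 percentage points
- k = 2: 2/40 = 5.0
- k = 3: 3/40 = 7.5
- k = 4: 4/40 = 10.0

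These are upper bounds for each k. They are reached only if every one of the k unknown events was truly at the level in question.

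**Step 4: between-arm effect**

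Let a and p be the numbers of participants truly understated on SYN120 and placebo. The distortion of the difference in proportions is (a − p)/40. With a = p = 3 it is zero. With a = 3 and p = 1 it is 2/40 = 5.0 points in favour of SYN120. With a = 1 and p = 3 it is 5.0 points against it. The documents support no particular values of a and p.

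**The case against.** The strongest reply is that the rule is narrow and may rarely operate.

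- **Scope.** It governs one column of one family of tables. Event counts by level and MedDRA-term counts do not depend on it, and TEAEs leading to discontinuation or death have their own incidence lines.
- **Conditions.** A participant must have a second event with a known level below the top. Someone whose only event is ungraded is not shown as milder.
- **Frequency.** Completion of the adverse event form, including the relatedness judgement, is left by Protocol 8.3 to guidelines that are not among the documents. Whether unknown is a permitted entry for severity or relatedness cannot be determined. Protocol 8.9.2 asks for a causality assessment on serious events, Protocol 8.4 requires follow-up or a justification for its absence, and participants who stop drug stay on study.
- **Use.** No test of worst-grade distributions is planned.
- **Remedy.** Recoding every unknown as severe in the main tables would replace one assumption with its opposite.

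All of this stands as a limit on scope and size, and the last point shapes the fix. None of it justifies ranking unknown lowest. Event counts do not repair the participant proportions, because they do not show whose event was ungraded. Protocol 8.4 itself accepts loss to follow-up as an end to adverse event follow-up, so an unknown outcome is a foreseeable entry.

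A reader might infer more: that all the adverse event tables hide unknowns, or that the plan makes SYN120 look safer than placebo. The documents do not support either. The rule is confined to the worst-grade column and is the same in both arms. Protocol 10.7 contemplates higher withdrawal on SYN120, but it gives no rate and does not link withdrawal to missing event attributes. Nor does the rule extend to the any-severe and any-related endpoints: there the SAP is silent, which is a gap and not a stated convention.

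**Conclusion.** The point holds for the participant-level worst-grade summary in SAP 3.9.1. For all five characteristics, a participant with both graded and ungraded events is counted at the worst known level. The error runs in one direction, and no sensitivity summary reveals it.

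The size is 2.5 percentage points per affected participant, assuming 40 per arm in the safety sample. How many will be affected cannot be derived, so the 2.5 to 10.0 point range is the weight of an assumed one to four participants and not a forecast. Understatement within an arm requires an unknown event truly worse than the participant's worst known one. Bias between arms also requires such participants to be unevenly split, and it could then run either way.

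This is a cheap improvement to safety reporting. It does not affect efficacy inference or power.

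**What to change.** In SAP 3.9.1:

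1. Delete the parenthetical that ranks unknown as not worst.
2. For each of the five characteristics, add an unknown row. It holds participants who have any unknown level and whose worst known level is below the top, together with those who have no known level. The SAP should state the order of levels so that the top one is defined.
3. Add one supplementary summary that counts unknown severity as severe and unknown relatedness as at least possibly related. Apply it also to incidence endpoints (b) and (d) in SAP 3.2.2 and 3.9.1, which closes the gap there.
4. Footnote the number of events so counted, by arm.

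Readers can then see the reported proportion and its upper bound together. The cost is one or two extra rows per characteristic, the supplementary summary, and slightly higher severe and related proportions in that summary when attributes are missing. No new data are needed. If no attribute is unknown, the proportions do not change.
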